The effect of deferasirox on growth and development was studied in the four-year extension of the phase III trial, Study CICL670A107, in pediatric patients with β-thalassemia major and transfusional iron overload (Cappellini MD, et. al., Blood 2011). Height, weight, growth, and pubertal stage (female breast development, male testes volume and pubic hair) were analyzed annually. The study results indicated that growth and sexual development were not impaired and progressed normally during long-term deferasirox treatment, thus suggesting that iron chelation with deferasirox abates the inhibitory effects of iron overload. However, this positive

effect of deferasirox has been not studied in NTDT pediatric patients and therefore it requires confirmation.

Because of the chronic nature of chelation therapy and the importance of patient compliance, an improved deferasirox formulation for oral administration has been developed. The film coated tablet (FCT) to be used in this study contains the same active substance but has been strength-adjusted to achieve comparable exposure to the currently approved dispersible tablet.

The purpose of this observational study is to provide further data, in addition to that obtained from the THALASSA trial, for the assessment of the safety of deferasirox in NTDT pediatric patients with documented iron overload as defined in a local product label. In addition, the assessment of growth in this patient population and sexual development of children between age ≥ 10 to <18 will be performed.

Patients enrolled into this study will be permitted to use deferasirox dispersible tablets or the new film coated tablets. Patients will be allowed to change formulation under the advice and guidance of the Investigator.

The study represents a key component of the active surveillance program for deferasirox. The monitoring of pediatric patient safety in actual practice settings will provide additional knowledge about the incidence and management of important ADRs.

A post-authorization safety study (PASS) is defined in Directive 2001/83/EC (DIR) Art 1(15) as any study relating to an authorized medicinal product conducted with the aim of identifying, characterizing or quantifying a safety hazard, confirming the safety profile of the medicinal product, or of measuring the effectiveness of risk management measures.

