7.1 Study design

This study is a registry of pediatric patients with non-transfusion dependent thalassemia conducted in response to a post-approval commitment to the US FDA for an observational study in this population in order to assess long-term exposure and safety of deferasirox. (PMR 1994-4: "Establish a registry of children (aged 10 to <18 years old at enrollment) with NTDT and treated with deferasirox for documented iron overload. Study CICL670E2422 will follow at least 40 children for up to 5 years to assess and analyze the long-term safety of treatment with deferasirox, including an assessment of growth, compared to children on a regular transfusion program receiving deferasirox (based on historical data)").

This study is non-interventional and does not impose a therapy protocol, diagnostic/therapeutic interventions or a visit schedule. However, a minimum of quarterly visits are suggested. Patients

will be treated with deferasirox in accordance with the local (country-specific) deferasirox prescribing information.

The definition of non-interventional study is provided in Article 21 of Directive 2001/20/EC: "A study where the medicinal product(s) is (are) prescribed in the usual manner in accordance with the terms of the marketing authorization. The assignment of the patient to a particular strategy is not decided in advance by a study protocol but falls within the current practice and the prescription of the medicine is clearly separated from the decision to include the patient in the study. No additional diagnostic or monitoring procedures shall be applied to the patients and epidemiological methods shall be used for the analysis of the collected data". In this context it is considered important to clarify that interviews, questionnaires and blood samples may be considered as normal clinical practice (EMEA 2008).

The study will take place in actual practice setting and will monitor patients treated with deferasirox according to the local (country-specific) prescribing information. The study will be based on primary data collection directly from healthcare professionals.

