The enrollment is defined as the patient's entry into the study; which is the point at which informed consent form is signed. Data will be collected on a minimum of 40 eligible pediatric patients who signed informed consent. These patients should be aged ≥ 10 to <18 years at enrollment, are diagnosed with non-transfusion dependent thalassemia and require to be treated with deferasirox or started deferasirox treatment 12 months or less prior to enrollment. These patients will be followed for up to 5 years from the start of deferasirox treatment. Retrospective data collection will be done for patients whom have started deferasirox 12 months or less prior to enrollment.

The baseline is defined as the timeframe before the patient starts treatment with deferasirox.

In patients who have protocol specified assessments performed prior to the date of first deferasirox treatment, the baseline data will be collected if it is within the following timeframe prior to the date of starting deferasirox treatment (see also table 7-2):

- 1.5 months for all laboratory assessments
- 6 months for vital signs, weight, height, LIC, ECG, ECHO, CMR, ocular and audiometry assessments
- 12 months for pubertal assessments (Tanner stage).

Post baseline data will be collected from the start date of deferasirox and then on for five years.

Investigational treatment

Deferasirox dispersible tablets

Deferasirox dispersible tablet is currently marketed in three dosing strengths (125, 250, 500 mg) and is dosed based on body weight. The currently approved dose range is up to 40 mg/kg/day.

Deferasirox dispersible tablets prescribed by physicians in actual practice setting will be used in accordance with the local label.

Initial deferasirox dose 10 mg/kg/d, 7 d/wk in accordance with the deferasirox prescribing information. Dose titration of deferasirox may be performed based on LIC levels as measured by magnetic resonance imaging (MRI) and/or SF levels and safety markers in steps of 5–10 mg/kg/d as defined by local label requirements.

Deferasirox Film Coated Tablets (FCTs)

Because of the chronic nature of chelation therapy and the importance of patient compliance, an improved deferasirox formulation for oral administration has been developed.

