If approved in the country, FCT may be used in this study. It contains the same active substance but has been strength-adjusted to achieve comparable exposure to the currently approved dispersible tablet. FCT is available in three dose strengths (90 mg, 180 mg, and 360 mg) and is dosed based on body weight. The FCT can be taken with or after a light meal. Initial FCT dose is 14 mg.kg/d, 7d/wk according to FCT prescribing information. Dose adjustments will be based on serum ferritin levels and the investigator's judgement. Dose adjustments based on safety are allowed at any time point in the study and will be in increments of 3.5-7 mg/kg/day. Throughout the study, the maximum dose of FCT will be 28 mg/kg/day.

Table 7-1 Dose conversion between dispersible tablets and film coated tablets

Deferasirox dispersible tablets	Deferasirox film-coated tablets	
Dose range: 10-40mg/kg; calculated and rounded to the nearest whole tablet size.	Dose range: 7-28mg/kg; calculated and rounded to the nearest whole tablet size.	
Dose adjustment: increments of 5-10mg/kg	Dose adjustment: increments of 3.5-7mg/kg	
Deferasirox DT therapeutic dose range:	Deferasirox FCT therapeutic dose range:	
10mg/kg	7mg/kg	
20mg/kg	14mg/kg	
30mg/kg	21mg/kg	
40mg/kg (max. recommended dose)	28mg/kg (max. recommended dose)	
Calculated dose example for 50kg patient	Calculated dose example for 50kg patient	
receiving deferasirox DT 30mg/kg:	receiving deferasirox FCT 21mg/kg:	
30mg/kg * 50kg = 1500mg/day	21mg/kg * 50kg = 1050mg/day	
Three (3) 500mg tablets	Three (3) 360mg tablets	

Deferasirox Administration

The investigational study drug used in this trial is deferasirox (ICL670). It will be provided as dispersible tablets for oral use or as film coated tablets for oral use.

Deferasirox (company research code: ICL670) is an orally active chelator that is highly selective for iron (III). It is a tridentate ligand that binds iron with high affinity in a 2:1 ratio. Two molecules of deferasirox form a complete complex with Fe³⁺.

The high potency of deferasirox in mobilizing tissue iron and promoting iron excretion was demonstrated both in vitro and in vivo model systems (Nick 2003). Deferasirox is eliminated from the body by hepatic glucuronidation and biliary excretion.

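### Section 7.1 gives starting doses for the two deferasirox formulations that differ two-fold on the protocol's own conversion scale, without explanation

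*Protocol*

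**What the plan says.** Protocol Section 7.1 describes two formulations of the same drug, both allowed in the registry, and prints a starting dose for each.

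- Dispersible tablet: "Initial deferasirox dose 10 mg/kg/d, 7 d/wk in accordance with the deferasirox prescribing information". It is "currently marketed in three dosing strengths (125, 250, 500 mg").
- Film-coated tablet: "Initial FCT dose is 14 mg.kg/d, 7d/wk according to FCT prescribing information". "FCT is available in three dose strengths (90 mg, 180 mg, and 360 mg").

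The FCT paragraph says that this formulation was "strength-adjusted to achieve comparable exposure to the currently approved dispersible tablet". Table 7-1, headed "Dose conversion between dispersible tablets and film coated tablets", follows directly. It pairs DT 10, 20, 30 and 40 mg/kg with FCT 7, 14, 21 and 28 mg/kg, and pairs dose steps of 5 to 10 mg/kg with steps of 3.5 to 7 mg/kg.

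Three other statements set the context.

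- Section 5 lets patients switch: "Patients will be allowed to change formulation under the advice and guidance of the Investigator".
- Section 7.1 says that patients "will be treated with deferasirox in accordance with the local (country-specific) deferasirox prescribing information".
- Section 7.3 (Treating the Patient) leaves the starting dose to the physician and the local label, and has it recorded on the dosing form.

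**The concern.** If the two formulations are meant to deliver comparable exposure once the strength adjustment is made, one would expect their starting doses to sit on the same row of the conversion table. They do not. The DT start is the first row of Table 7-1 and the FCT start is the second. Each sentence points to prescribing information, but neither that attribution nor any other text says why a child starting on FCT should begin at twice the DT-equivalent dose.

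The wording matters because this is a safety registry in children, with creatinine and ALT increases among its secondary endpoints. A site that took both sentences at face value would start otherwise similar patients at clearly different effective doses depending on formulation. A reader of the protocol cannot tell whether that is intended or is a slip.

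The unit in the FCT sentence is also misprinted, with a full stop where the first slash belongs. That is editorial: the sentences that follow in the same paragraph give the dose steps and the maximum correctly in mg/kg/day.

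**Working it through.** **Inputs (all from Protocol Section 7.1 and Table 7-1)**

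- DT start: 10 mg/kg/d
- FCT start: 14 mg/kg/d (reading the unit as intended)
- Table 7-1 pairs (DT, FCT): (10, 7), (20, 14), (30, 21), (40, 28); steps (5, 3.5) and (10, 7)
- Tablet strengths: DT 125, 250, 500 mg; FCT 90, 180, 360 mg

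**Step 1. Reproduce the table's conversion factor.** Factor = FCT dose / DT dose.

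- Dose rows: 7/10 = 14/20 = 21/30 = 28/40 = 0.70
- Steps: 3.5/5 = 7/10 = 0.70

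The table's worked example at 50 kg also reproduces. For DT, 30 × 50 = 1500 mg, which is three 500 mg tablets. For FCT, 21 × 50 = 1050 mg, rounded to three 360 mg tablets (1080 mg).

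**Step 2. Put both starts on the DT scale using the table.** DT-equivalent = FCT dose / 0.70.

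- FCT start: 14 / 0.70 = 20 mg/kg/d of DT
- Ratio to the DT start: 20 / 10 = 2.0

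**Step 3. Repeat with the marketed tablet strengths.**

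- 90/125 = 180/250 = 360/500 = 0.72
- FCT start: 14 / 0.72 = 19.4 mg/kg/d of DT
- Ratio to the DT start: 19.4 / 10 = 1.94

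**Step 4. Go the other way.** The FCT equivalent of the stated DT start is 10 × 0.70 = 7 mg/kg/d, the first row of Table 7-1.

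**Step 5. Illustrate at the 50 kg weight used in Table 7-1, before rounding to tablets.**

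| Start | mg/day | DT-equivalent mg/day (÷ 0.70) |
|---|---|---|
| DT 10 mg/kg | 500 | 500 |
| FCT 14 mg/kg (as stated) | 700 | 1000 |
| FCT 7 mg/kg (matching the DT start) | 350 | 500 |

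**Step 6. Compare each start with its own maximum in Table 7-1.** DT: 10/40 = 25%. FCT: 14/28 = 50%. The same factor of two appears.

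The gap does not depend on which of the protocol's two conversion routes is used. No row of Table 7-1 is broken: FCT 14 mg/kg is a listed dose, and the table names no starting dose. The conflict lies between the two starting-dose sentences once they are put on one scale.

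**The case against.** The best reply is that these sentences do not set anyone's dose. The study is non-interventional, Sections 7.1 and 7.3 hand the starting dose to the physician and the local label, and actual doses are recorded and summarised as given. That stands, and it is the main reason why the point is minor. It does not remove the inconsistency: the protocol chose to print both starts, and it gives no reason for the difference.

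A second reply is that two labels may properly recommend different starts, and that a conversion table for comparable exposure does not oblige them to agree. That also stands. The FCT label is not among the documents, so a reader might infer that 14 is wrong and 7 is right, but the protocol cannot settle that. It supports a request to reconcile or explain, and no more.

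A reader might further infer that patients who switch would be doubled by mistake. The protocol does not support that strongly. Table 7-1 exists for the switch and comes straight after the FCT paragraph, switching is under the investigator's guidance, and weekly creatinine checks are recommended for the first month after therapy is started or modified.

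It is also tempting to set the FCT start against the doses of the randomised NTDT study described in Section 5. That section does not state which formulation those doses refer to, so the comparison would rest on an assumption and shows nothing about this protocol.

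Finally, few new starts may remain to be affected. Version 04 is dated 10 June 2020 and data collection is planned to end on 30 July 2025, so a patient followed for a full five years would have started by about July 2020. This limits the benefit of a correction without making the text right.

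**Conclusion.** The inconsistency is real and is in the current body text. On the protocol's own scale the stated FCT start is 2.0 times the stated DT start (1.94 times by tablet strengths), for two formulations described as giving comparable exposure, and the difference is not explained.

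The result rests on two things: reading the misprinted FCT unit as mg/kg/d, which the rest of the paragraph supports, and taking Table 7-1 or the tablet strengths as the exposure conversion, which is how the protocol presents them.

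It should not be read as a mandated overdose, since the local label and physician discretion govern dosing. No endpoint, analysis set or sample-size figure depends on it. Severity is minor, with a small patient-safety benefit from clearing it up.

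**What to change.** 1. Check the FCT starting dose in Section 7.1 against the NTDT section of the FCT prescribing information.
2. If the label gives the DT-equivalent, replace 14 with 7 mg/kg/d. If it supports 14, keep it and add a sentence saying why the FCT and DT starts differ.
3. Correct the unit to mg/kg/d in the same edit.
4. Inform sites of the outcome in a short letter.

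The cost is one or two sentences in Section 7.1 and the letter. Endpoints, analyses and data collection do not change.

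### Section 7.1 gives film-coated and dispersible tablet starting doses that differ twofold under the protocol's own conversion, and a fixed film-coated maximum not tied to the local label

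*Protocol*

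**What the plan says.** Section 7.1 of the protocol treats the two formulations in separate paragraphs.

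- **DT start:** "Initial deferasirox dose 10 mg/kg/d, 7 d/wk in accordance with the deferasirox prescribing information".
- **DT titration:** steps of 5–10 mg/kg/day, guided by liver iron, serum ferritin and safety markers, "as defined by local label requirements". A separate sentence puts DT use as a whole under the local label.
- **FCT premise:** the tablet is "strength-adjusted to achieve comparable exposure to the currently approved dispersible tablet". It may be used where it is approved in the country.
- **FCT start:** "Initial FCT dose is 14 mg.kg/d, 7d/wk according to FCT prescribing information".
- **FCT adjustment:** "Dose adjustments will be based on serum ferritin levels" and on the investigator's judgement. Safety-based changes are allowed at any time, in steps of 3.5–7 mg/kg/day.
- **FCT maximum:** "Throughout the study, the maximum dose of FCT will be 28 mg/kg/day".

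Table 7-1 pairs DT 10, 20, 30 and 40 mg/kg with FCT 7, 14, 21 and 28 mg/kg. Section 5 adds: "Patients will be allowed to change formulation under the advice and guidance of the Investigator".

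Two general statements also apply. Section 7.1 says that the study is non-interventional and dictates no treatment regimen. Section 7.3 (Treating the Patient) leaves starting dose, adjustments and interruptions to the physician and the country's prescribing information, with no exception for either formulation.

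**The concern.** If the two tablets give matched exposure and Table 7-1 is the conversion, the two starting doses for one population should convert into each other. They do not. Both are attributed to prescribing information, and the protocol does not explain the gap.

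The FCT paragraph also reads more like a study dosing rule than the DT paragraph does. It has a fixed ceiling for the whole study and fixed adjustment steps, with no local-label clause on either. That fits poorly with a registry that is meant to observe local practice. Amendment 4 turned the ferritin and liver-iron stopping rules into recommendations because such rules cannot be enforced in a non-interventional study. The FCT maximum in the same section was not reworded in that way.

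The stake is clarity for sites treating children. A physician starting a child on FCT finds a number in the FCT paragraph, a different one by converting the DT start, and a general label rule elsewhere. Section 9 asks for closer watch for overchelation when doses are high and ferritin is near target, so unambiguous dosing text has a plausible safety benefit.

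**Working it through.** **Inputs, all from Section 7.1 and Table 7-1:** DT start 10 mg/kg/day; FCT start 14 mg/kg/day; DT steps 5–10 and FCT steps 3.5–7 mg/kg/day; approved DT range up to 40 mg/kg/day; FCT maximum 28 mg/kg/day; FCT tablet strengths 90, 180 and 360 mg.

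**1. Reproduce the conversion.** Factor = FCT dose / DT dose, row by row:

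| DT (mg/kg) | FCT (mg/kg) | Factor |
|---|---|---|
| 10 | 7 | 0.7 |
| 20 | 14 | 0.7 |
| 30 | 21 | 0.7 |
| 40 | 28 | 0.7 |

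The table is internally consistent, with a constant factor of 0.7.

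**2. Check the steps and the maximum.** 5 × 0.7 = 3.5 and 10 × 0.7 = 7, so the FCT steps are the converted DT steps. 40 × 0.7 = 28, so the FCT maximum is the converted top of the approved DT range. Neither number conflicts with the DT text.

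**3. Check the starts.**

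- DT start as FCT: 10 × 0.7 = 7 mg/kg/day.
- FCT start as DT: 14 / 0.7 = 20 mg/kg/day.
- Ratio: 14 / 7 = 20 / 10 = 2.0.

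The start is the only FCT figure that does not follow from its DT counterpart.

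**4. What it means in tablets.** For a 50 kg child, the weight used in Table 7-1's own example:

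- 7 × 50 = 350 mg, rounding to one 360 mg tablet.
- 14 × 50 = 700 mg, rounding to two 360 mg tablets (720 mg).

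**5. Compare the label clauses.**

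| Element | DT paragraph | FCT paragraph |
|---|---|---|
| Start | tied to prescribing information | tied to prescribing information |
| Adjustment | tied to local label | ferritin, judgement and safety; no label clause |
| Maximum | approved range quoted; use under local label | fixed study-wide figure; no label clause |

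The missing clause therefore concerns FCT adjustment and maximum. It does not concern the start, where the two paragraphs run parallel.

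**The case against.** The strongest answer is that the local label already governs FCT. Section 7.1 says generally that patients are treated under local prescribing information, and Section 7.3 repeats this for start and adjustment without distinguishing formulations. A ceiling of 28 mg/kg/day does not contradict a lower local cap, and it is only the converted DT figure. The FCT start cites prescribing information, as the DT start does, and the adjustment text does allow for safety. Table 7-1 is titled as a conversion table, so it naturally governs switches, and an initial dose naturally means starting treatment. All of this stands, and it is why the point is minor.

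It does not remove the mismatch in starts. The general label rule does not tell a site why two matched formulations should begin a factor of two apart, and neither paragraph does either.

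Three stronger readings are tempting but not supported:

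- **That 14 or 28 mg/kg/day exceeds the NTDT label.** The protocol gives no label start or maximum specific to NTDT, so this cannot be shown. Nor can it be shown which of the two starts is wrong, since each source might say what is attributed to it.
- **That the FCT paragraph overrides the local label.** It omits a clause; it does not cancel the general rule.
- **That these doses are too high against the earlier randomized NTDT trial.** Section 5 does not name the formulation for that trial's doses, and a past trial's doses are not a dosing rule of this study.

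**Conclusion.** The point holds as a minor inconsistency in the dosing text. The stated FCT start is exactly 2.0 times the stated DT start after conversion, for the same children and without a reason. This rests only on Table 7-1 and the protocol's statement that exposure is matched. Separately, the FCT maximum and adjustment steps lack the local-label clause given to DT titration, although the general label rule in Sections 7.1 and 7.3 still covers them.

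A reader might infer that children will be overdosed or that the safety results will be distorted. The document supports neither. The maximum is a ceiling and not a target, dosing remains with the physician and the local label, and Section 9 makes overdose and off-label use reportable as adverse events. No endpoint or analysis is affected.

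**What to change.** Four wording changes in the FCT paragraph of Section 7.1:

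1. Replace the FCT start of 14 mg/kg/day with 7 mg/kg/day, the Table 7-1 equivalent of DT 10, or with the local NTDT label start if that differs.
2. Add "as defined by local label requirements" to the FCT dose adjustments, as for DT.
3. Reword the maximum so that the dose is not to exceed the local label maximum for NTDT, and in no case 28 mg/kg/day. This keeps a ceiling in place.
4. State that patients who change formulation are converted by Table 7-1, so that the initial-dose sentence is not applied to a switch.

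The sponsor should check the first change against the NTDT label before issuing it. The cost is a protocol wording change and a letter to sites, with no new data, patients or procedures.
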